6.2 Number of Subjects to be Enrolled

Sample size calculations were performed to determine the number of patients needed for each of the 36 study groups that will provide reasonable estimates of the population mean and SD for each measurement (35). There are several assumptions associated with these calculations:

- All variables should be normally distributed. Any variable that does not meet the normality assumption will need to undergo a mathematical transformation.
- At least 80% of the submitted echo studies will contain all the necessary images to perform each of the study measurements. In other words, for every group of 100 study patients, one would expect at least 80 studies in which each particular measurement can be made.

Assuming a normal distribution, a confidence interval for the SD is given by the following equation:

$$\sqrt{\frac{(n-1)s^2}{\chi_{n-1}^{2(1-\frac{\alpha}{2})}}} \leq \sigma \leq \sqrt{\frac{(n-1)s^2}{\chi_{n-1}^{2(\frac{\alpha}{2})}}}$$

We can minimize the width and solve for n such that

$$\sqrt{n-1} \left(\frac{1}{\sqrt{\chi_{n-1}^{2(\frac{\alpha}{2})}}} - \frac{1}{\sqrt{\chi_{n-1}^{2(1-\frac{\alpha}{2})}}} \right) < r$$

where r is some proportion of the observed point estimate of the SD. For $n = 80$ and $\alpha = 0.05$, the width of a 95% confidence interval would be 32% ($r = 0.32$) of the observed SD. In addition, the margin of error is calculated as

$$\frac{z_{\frac{\alpha}{2}} \sigma}{\sqrt{n}}$$

For $n = 80$, the margin of error for the mean would be 22% of the observed SD. Given the 80% echo quality assumption discussed above, each of the 36 study groups should have 100 patients in order to satisfy the requirements for the 95% confidence interval and margin of error for the mean. Thus the total sample size for the study is 3600 patients.

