6.1.1 Derivation of Mean and Standard Deviation

The mean and SD of a given measurement will be derived for each of the 36 study groups described above. For a given group, the mean (E) and SD of an echo measurement (Y), given the BSA, are as follows:

$$E(Y|BSA) = \mu_y + \rho \frac{\sigma_y}{\sigma_{BSA}} (BSA - \mu_{BSA})$$

$$SD(Y|BSA) = \sigma_y \sqrt{1 - \rho^2}$$

where ρ is the correlation between the echo measurement and BSA in each group, σ_y and σ_{BSA} are the group SDs of the echo measures and BSA respectively, and μ_{BSA} is the group mean BSA. These quantities can be estimated using each group's observed data.

The equations above are equivalent to fitting a linear regression model of the form

$$Y = \alpha + \beta(BSA)^n$$

The power n of BSA will be determined so that the transformed BSA and echo measurement will have approximately a linear relationship. For example, the diameters of the great vessels and the semilunar valve orifices have been found to relate most closely in a linear fashion to $BSA^{0.5}$ (9).

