Once the best available method for obtaining BSA has been determined and the simplest, best-fit model has been identified for each of the variables, the next step will involve examination for non-constant variance (heteroscedasticity) for each regression. In general, all of these relationships are anticipated to manifest heteroscedasticity characterized by a progressively but not necessarily linearly increasing variance with increasing BSA. Under these circumstances, the method described by Altman (33) provides a simple and adequate approach to generate a constant variance relationship. Although more complex methods (log or other transforms of one or both variables) have been described, they lack a physiologic basis and do not generally outperform the Altman technique. If there are individual variables for which the Altman methodology fails to adequately eliminate heteroscedasticity, the Lambda-Mu-Sigma method described by Cole and colleagues (34) will be adopted for those specific variables.

The Z-scores for each of the 36 study groups (based on age, gender, and race) will be compared using a t-test and adjusted for multiple comparisons. Groups which are not statistically different may be combined. For example, if the Z-scores for a particular measurement are not statistically different between males and females, the two groups may be combined and a new estimate of the mean and SD for the combined group will be determined.

The potential relationship of each set of Z-scores to height, weight, and BMI will also be examined using linear regression, and the potential for differences related to ethnicity will be examined using analysis of variance.

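### The 32% interval width for the SD in Section 6.2 holds only for an SD that is constant over BSA within a group, whereas Section 6.1.2 expects to use an SD that varies with BSA, whose precision is not stated

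*Protocol*

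**What the plan says.** Section 6.2 sizes each of the 36 groups on the precision of the mean and the SD. It expects that "for every group of 100 study patients, one would expect at least 80 studies in which each particular measurement can be made". For the SD it uses the chi-square interval for a single normal sample: "Assuming a normal distribution, a confidence interval for the SD is given by the following equation". At n = 80 it concludes that "the width of a 95% confidence interval would be 32" percent of the observed SD. For the mean, "the margin of error for the mean would be 22% of the observed SD". Dividing 80 by 0.8 gives 100 per group, and 36 groups give 3600.

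Section 6.1.1 states that "The mean and SD of a given measurement will be derived for each of the 36 study groups described above". Its formula, σ_y√(1−ρ²), contains no BSA term, so the SD is the same at every BSA within a group.

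Section 6.1.2 then plans to examine each regression for non-constant variance and says what it expects to find: "all of these relationships are anticipated to manifest heteroscedasticity characterized by a progressively but not necessarily linearly increasing variance with increasing BSA". For that situation, "the method described by Altman (33) provides a simple and adequate approach to generate a constant variance relationship", with the Lambda-Mu-Sigma method as fallback for variables where this fails. The title of reference 33 describes reference centiles built from absolute residuals. The same section allows groups that do not differ to be combined.

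**The concern.** The chi-square interval describes one SD estimated from one sample with a common variance. The plan expects that condition to fail for all its measurements and names a method that replaces the single SD with a curve over BSA. Such a curve has at least two estimated coefficients, and it is least certain away from the mean BSA. The only SD precision figure in the protocol therefore belongs to an estimator that the plan itself expects to set aside.

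The SD is half of the primary aim and the denominator of every Z-score. The age groups are broad (one runs from 1 month to under 3 years), so many children will lie well away from their group's mean BSA. A reader who takes 32% as the precision of the published SD would be too optimistic for them.

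**Working it through.** **Inputs from the protocol.** n = 80 usable studies per group, two-sided 95% interval, normal errors.

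**Inputs that I assume, because the protocol gives none.** The Altman fit is linear in BSA and made separately in each group. BSA within a group is uniform or normal. The SD follows 1 + g·x, with x the BSA in SD units from the group mean and g = 0, 0.15 or 0.25.

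**Step 1: the protocol's own figures.**
- Width = √79 × (1/√χ²(0.025; 79) − 1/√χ²(0.975; 79)) = 0.319, printed as 32%.
- With 78 degrees of freedom, after fitting the line in Section 6.1.1, it is 0.321.
- Margin for the mean = 1.96/√80 = 0.219, printed as 22%.
- 80/0.8 = 100, and 36 × 100 = 3600.

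All reproduce.

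**Step 2: width for an absolute-residual fit.** For normal errors the mean absolute residual is σ√(2/π) and its variance is σ²(1 − 2/π). The SD estimate is √(π/2) times the fitted absolute residual. With a flat true SD, at distance d from the group mean BSA (in SDs of BSA):

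relative 95% width ≈ 2 × 1.96 × √((π/2 − 1)/n) × √(1 + d²)

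| n | d = 0 | d = 1 | d = 1.5 |
|---|---|---|---|
| 80 | 0.331 | 0.468 | 0.597 |
| 100 | 0.296 | 0.419 | 0.534 |
| 160 | 0.234 | 0.331 | 0.422 |

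**Step 3: does the result survive a real gradient?** Simulated groups of 80 were fitted by ordinary least squares for both the mean and the absolute residuals. The 2.5–97.5 percentile spread of estimated over true SD was recorded.

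| Position | g = 0 to 0.25, uniform BSA | g = 0 to 0.25, normal BSA |
|---|---|---|
| Group mean BSA | 33–34% | 33–34% |
| 1 SD from mean | 46–49% | 47–51% |
| 1.5 SD from mean | 54–78% | 54–81% |

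At 1.5 SD the wide values are at the low-BSA side and the narrow ones at the high-BSA side. With steeper gradients (SD tripling across the range) the width at the mean reaches 35%. With weighted fits and SD ratios of 1 to 3 across the range, the width at 1 SD is 43–48%. The result at 1 SD is therefore stable, and the result further out is not.

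**Step 4: keeping the constant-SD fit.** If a constant SD were fitted although the variance rises with g = 0.15 or 0.25, its sampling width would be about 33–36% rather than 32%.

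**Step 5: n for a 32% width under the flat-SD formula.** (2 × 1.96 × √(π/2 − 1) × √(1 + d²)/0.32)² gives about 86 at the mean and about 171 at 1 SD.

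**The case against.** The case on the other side is substantial.

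- **The 32% is not a miscalculation.** It reproduces, it fits the constant SD of Section 6.1.1, and it is almost right at the group mean BSA even under the Altman fit. This stands. A reader might infer an arithmetic error, but the formula is correct for its own model.
- **Section 6.2 claims nothing about precision at a particular BSA or at the ±2 threshold.** This also stands. The defect is that the stated figure does not belong to the expected SD model, not that a pointwise promise is broken.
- **The level of the variance fit is not stated.** Section 6.1.1 works by group, while Section 6.1.2 speaks of models for each variable. One fit over all groups (assumed n = 36 × 80 = 2880) would give about 5.5% at the mean BSA and 10% at 1.5 SD by the Step 2 formula. So the 47–50% is conditional on a per-group fit. Section 6.2, however, claims its precision for each of the 36 groups, so a per-group figure is the like-for-like comparison.
- **Groups may be combined, and 80 is a floor.** Merging two groups (n = 160) brings the width at 1 SD to about 33%; n = 100 brings it to about 42%. Combining is conditional on test results, so it cannot be counted on in advance.
- **The 47% might be only a zero-gradient value.** This does not stand: the simulation gives about the same figure for slopes up to 25%.
- **Altman is applied only after variance has been examined.** True, but the plan says what it expects that examination to show, for every relationship.

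A reader might also take 54–80% as what this design delivers at the ends of each group. The documents do not support that, because they give no BSA spread, SD slope or fitting weights. Other plausible inputs and end points give about 52% to over 100%.

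**Conclusion.** The concern holds in a limited form. The 32% is valid for an SD that is constant over BSA within a group. The plan expects that not to be the case, and Section 6.2 states no precision for the BSA-dependent SD that would replace it.

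Under a per-group linear Altman fit with 80 usable studies, the width is about 33–35% at the group mean BSA and about 47–50% at 1 SD from it. That is roughly 15 to 18 points above the stated figure at 1 SD. Values beyond 1 SD are scenarios, not findings. Combining groups, or fitting the variance model across groups, would narrow all of these widths.

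It does not follow that 3600 is the wrong sample size. The protocol sets no required width that the study would miss; it reports the width that n = 80 gives.

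**What to change.** 1. In Section 6.2, say that the 32% applies to a measurement whose SD is constant over BSA within a group. Add the expected per-group width under the Altman fit: about 33–35% at the group mean BSA and about 47–50% at 1 SD. Show the assumptions (linear fit within each group, n = 80), and label any range-end value as a scenario with its assumed SD slope and BSA spread.
2. Make Sections 6.1.1, 6.1.2 and 6.2 agree on whether the reported SD is constant or a function of BSA, and on whether the variance model is fitted per group, per combined group or across groups. If it is fitted on larger sets, state the precision for those sets.
3. Report each fitted SD with a bootstrap 95% interval over BSA, refitting both the mean regression and the absolute-residual regression in every resample.

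The cost is wording and a bootstrap run. The downside is a less favourable stated precision. No extra patients or data are needed, and the 3600 stays.

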6.3 Level of Significance

The primary aim of this study will be the estimation of the mean and SD of the normal population for the measurements listed in Section 4.3.1. When hypothesis testing is conducted for some secondary aims, the type I error probability will be 0.05. No adjustment will be made to account for comparing the groups with respect to more than one outcome variable. However, multiple comparison adjustments will be made to control the type I error when comparing study groups for the purpose of collapsing group categories.

6.4 Spurious Data Procedures

Consistency checks and range checks will be built into the data management system (DMS). This will allow many errors to be identified and corrected at the time of data entry. Queries regarding any problems with data will be sent to site coordinators regularly throughout the course of the study. Sites will also be monitored during the study. Therefore, spurious data are expected to be rare. Any data which are judged by the medical monitors to be definitely incorrect, and which cannot be resolved, will be set to missing.

The study report will indicate the number of subjects who have missing data on each study endpoint. For covariate-adjusted analyses, the number of subjects who have missing data on the covariates will be reported.

Throughout the study, the rate and reasons for data exclusion will be monitored by site and by measurement, and the Core Laboratory will provide monthly quality assessment data to each site. Any site with a high frequency of unacceptable data quality will be queried. If necessary, retraining will take place or the site may be barred from further participation in the study. If any measurement is absent in >20% of studies, the Study Submission Sub-Committee will address measures to improve acquisition of these data.

6.5 Deviation Reporting Procedures

Any modifications or deviations from the statistical plan described in this protocol will be documented in a "Revised Statistical Plan" document.

6.6 Subjects to be Included in Analyses

Echo measurements from all eligible subjects will be included in the analysis.

6.7 Data and Safety Monitoring Plan

The Data and Safety Monitoring Plan for this study will follow standard PHN monitoring principles. Oversight of data and safety is provided by the PHN DSMB, appointed by NHLBI. The DSMB, which meets at least biannually, is composed of experts in pediatric cardiology, congenital heart surgery, biostatistics and study design, and ethics, as well as a lay member. For this study, the DSMB will review study accrual, data quality, and protocol violations on a regular basis and make recommendations about study conduct to the Director, NHLBI.

7. DATA MANAGEMENT

An Electronic Data Capture (EDC) system will be used for the study that is designed to support reliable and secure data entry for clinical research purposes. The system also provides seamless integration of electronic Case Report Forms (eCRF) and paper-based Case Report Forms (CRF) within a single protocol if desired; implementation of protocol amendments; and SAS and XML study data exports.

7.1 Data Entry

Data can be entered directly from multiple study sites via a fully validated and 21 CFR Part 11 compliant, secure Web application and stored centrally. A configurable sample-based double data entry system is available. Data are entered by subject study identification number; names will not be linked with subject data in the database. Study sites will maintain records in secure areas linking the subject name with the identification number assigned for the study. Study sites will have full access to their own data and be able to view these data remotely. Study staff will not be able to view subject data associated with other sites.

The PHN Bioinformatics Grid provides the software tools and secure infrastructure for clinical sites to submit image studies and other PHN study data to a central study archive (the PHN Data Hub). Study images transmitted from the clinical sites are completely de-identified and anonymized through PHN software tools to remove any patient-specific information, and these are assigned PHN study blind identifiers (numbered identifiers provided by the DCC). Studies are de-identified with removal of all personal health information (PHI) or personally identifying information (PII) by PHN software at the clinical site and are electronically transferred to the PHN Data Hub hosted at Johns Hopkins University (JHU). The PHN Grid Portal provides role-based access control to review image studies and related study data from a web browser, to ensure that they are de-identified, and to route them to the PHN DCC and/or Core Laboratory for processing and analysis. All data transfers are completed through secure protocols using Hypertext Transfer Protocol Secure (HTTPS).

At JHU, de-identified image studies are stored in a dedicated PHN Data Hub and accessed by the PHN Portal database and web services that are password protected and encrypted. The system server holding the PHN data is separated from other JHU systems and can only be accessed by Information Technology staff specifically assigned to support the PHN (members of JHU and Booz Allen Hamilton contractor team supporting this work). No PHI is kept on the PHN Grid or Image/ECG Archive servers, nor can identity be derived by any combination of data contained within the PHN Grid platform.

Later in 2012, ECG data files will also be stored at the PHN Data Hub, leveraging open-source ECG management and analysis tools (ECG Grid) developed by JHU under the Cardiovascular Research Grid (CVRG) program. The ECG data will also undergo similar de-identification as the images before the data leave the clinical site and will be stored with the corresponding image and study data. Management and storage of the Subject relationship is performed externally and is not integrated by any mechanism that can associate the identifiers (typically 10 digit numbers) to a real patient. Only the clinical sites, as custodians of the patient data and physician-patient relationship, hold the information necessary to match patient-to-PHN identifier information.

7.2 Data Validation and Monitoring

Integrated into the data entry system are real time validations, including both inter- and intra-instrument data checks. Inconsistent or questionable values are flagged during entry, and an edit report is automatically generated to the data entry client. These edit reports provide the information necessary to investigate any data entry errors or resolved questions regarding out-of-range or questionable values. Second level query tracking allows monitors and data managers real time access to unresolved queries as well as the date and time of query generation and resolution.

7.3 Data Security and Integrity

All data changes are written to an audit trail. The audit trail identifies the data item by table, column and key field. The entry includes the user, date and time, as well as the old value and new value. Both patient related data as well as trial configuration data are written to the audit trail. Data are saved at regular intervals during data entry to prevent loss of information in the event of a disruption of the Internet connection. In the unlikely event of a major disruption, a backup connection allows full access to the DMS.

Several levels of security are employed to ensure privacy and integrity of the study data, including the following: Study access requires use of assigned user names and passwords. Individual roles and access levels are assigned by the study data manager. Passwords are changed regularly. Web-based entry uses secure socket layer (SSL) data encryption. Data will not be stored on laptop computers.

8. QUALITY CONTROL (QC) AND QUALITY ASSURANCE (QA)

The DCC has primary responsibility for QC/QA activities of the phenotypic data. The DCC also requires that the sites complete certain QC activities, most of which are monitored by the DCC. The key QC/QA activities are:

- Development of a Study Manual;
- Clearly formatted and carefully constructed Data Forms with clear, up-to-date manuals of instruction;
- Sign-Off Procedures for all CRFs;
- Central protocol training and certification of all site data collection staff with the use of standardized checklists;
- Data management training and certification of site personnel completing data entry and/or data management;
- Verification of patient eligibility;
- On-going monitoring of all protocols/data collection activities;
- Completion of reliability and/or pilot studies for key measurements as appropriate;

-
- Inclusion of repeat measurements, as feasible, in the course of the study; and
 - Monitoring visits to sites as required with pre-specified goals and/or remote monitoring activities.

The DCC may conduct site visits to the Core Laboratories to review QA and QC procedures and data transfer to the DCC. Review of central laboratory-related reports will be conducted at least monthly to identify overall or site-specific problems in data or specimen acquisition and reporting of results.

9. ETHICS AND HUMAN SUBJECTS CONSIDERATIONS

9.1 Potential Risks

Because this is a retrospective collection of de-identified demographic and clinical data, echo images, and ECGs from patients who have already undergone evaluation and testing, there are no significant procedural risks associated with the data collection.

9.2 Confidentiality, Protection against Risks

Investigators will take all reasonable measures to protect the confidentiality of subjects and their families, including the following:

Use of Subject ID numbers

Each subject is assigned a subject identification number (SID). All clinical research data are stripped of identifiers and labeled with the study number. The enrollment log with participant identifiers will be maintained at each site in a secured, locked location available only to the study staff. The subject's name and any other identifying information will not appear in any presentation or publication resulting from this study.

9.3 Potential Benefits

Because this is a retrospective collection of demographic and clinical data, echo images, and ECGs from patients who have already undergone evaluation and testing, and because prospective measurements will be performed on de-identified echo images, the study will not provide direct benefit to individual participants or families. The benefits are those to society as a whole in the improvement of knowledge of the causes or treatment of CHD, in the development of new diagnostic tests, and ultimately in the improvement of prognosis.

9.4 Risk/Benefit Ratio and Importance of Information to Be Obtained

The risk/benefit ratio is favorable for this study, and adverse events are not anticipated. The baseline risk is minimal because there are no therapeutic interventions. In addition, although an individual subject may not benefit from participation, the results of this study will make important contributions to the improvement of knowledge of the causes of CHD, in the development of new diagnostic tests, and ultimately in the improvement of treatment and prognosis.

